A user panel consisting of both newly injured as well as experienced people with SCI was established and involved in the early phase of the protocol development. All the participants were

¹ The completeness of the injury is graded according to the ASIA Impairment Scale (AIS). AIS is used to determine the degree of motor and sensory function below the level of the SCI. A complete or incomplete injury is defined as absence or presence of sensory and motor function in the most caudal sacral segment. A = complete; B = sensory incomplete without motor function > 3 levels below the motor level of injury on both sides of the body; C = motor incomplete, with preserved motor function below the level of injury and where > 50% of the key muscles below the injury level have a degree < 3 by MMT; D = motor incomplete with preserved motor function below the level of injury and where > 50% of key muscles below the injury level have a degree > 3 by MMT; E = normal sensory and motor function in all segments.

hospitalized at CSCI when they were interviewed about their perception of the present health promoting practice at the clinic. The user panel called for more information in the early phase of rehabilitation about cardiovascular risk, PA and diet as well as more support and guidance about being physical active and appropriate diet, which is the main aim of the project.

Primary study. A systematic interdisciplinary multimodal intervention which, as a part of usual care, facilitates PA, healthy diet and maintenance after discharge through strategic patient education, with the aim of decreasing cardiovascular risk

This pre-post study includes all patients with a new SCI who are admitted at CSCI during a period of 12- 18 months including follow up 6 months after discharge from primary rehabilitation.

Approximately 70 patients with a new SCI are admitted to CSCI annually and with a great variation in length of rehabilitation. Therefore complete data sets from admission to follow up are expected for approximately 50-60 patients during this period.

Intervention

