and blood samples describing metabolic profile. BMI is part of usual care while body composition evaluated by a body scan (DEXA) is part of usual care at discharge, and therefore the study applies one additional scan to the patients. Measure of shared decision making related to the two patient decision aids for PA and healthy diet (Shared Decision Making Questionnaire (SDM-Q-9)) is only used at discharge. Amount of physical activity (Leisure Time

Physical Activity Questionnaire for people With Spinal Cord Injury (LTPAQ-SCI)), self- assessed ability to be physically active (Exercise Self Efficacy Scale for people with Spinal Cord Injury (ESES)),

The following assesments were not a part of standard rehabilitation: Physical capacity is assessed by exercises already being a part of standard rehabilitation and the assessment is non-invasive while a mask covering nose and mouth measures the patients expired air. The patients ventilation is not impaired and the patient can terminate the test at any time. Physical activity is measured by an activity monitor attached to the patient's chest by two surface electrodes and is non-invasive. The monitor is individually calibrated to the patients by heart rate measures obtained during the assessment of physical capacity. *This outcome was not implemented as intended, due to low feasibility of the procedures needed for individual calibration in the clinical setting.*

The patients will perform the daily activities they would do regardless of the assessment and no new task will be required. The assessments of physical capacity and physical activity will be assessed twice to measure the reproducebility of the measurements. A blood sample (5ml) will be collected at the same time as a standard blood sample related to standard rehabilitation is collected. In this way only one needlestick will be applied to the patient. The analysis describing metabolic profile will be performed immediately after and the blood sample will not be stored.

Outcome measures evaluating the intervention comprises furthermore more of the following tertiary outcomes:

Tertiary outcomes

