Figure 1. Timeline and outcome measures used in the historic control study (A) at the Spinal Cord Injury Center of Western Denmark (SCICWD) and the Department for Spinal Cord Injuries in Eastern Denmark (DSCIED). Timeline and outcome measures used in the intervention study at DSCIED (B) (Source: Protocol article)

VCR: Center for Spinal Cord Injury, Western Denmark; **CSCI:** Clinic for Spinal Cord Injuries, Eastern Denmark; **BMI:** Body Mass Index; **SCIM:** Spinal Cord Injury Independence Measure; **ISNCSCI:** International Standards for Neurological Classification of Spinal Cord Injury; **PHQ-2:** Patient Health Questionnaire- 2; **QOL SCI:** International SCI Quality of Life Basic Data Set; **LTPAQ-SCI:** Leisure Time Physical Activity Questionnaire for people with Spinal Cord Injury; **ESES:** Exercise Self Efficacy Scale ; **AH** Actiheart (accelerometer); **VO2peak:**peak oxygen uptake; **DXA:** Dual-energy X-ray Absorptiometry; **MP:** Metabolic profile; **NORMON:** Nordic monitoring of diet, physical activity and overweight; **SDM-Q-9:** 9-item Shared Decision Making Questionnaire

Outcome measures

All outcome measures will be collected at admission, discharge and follow-up 6 months after discharge. At CSCI data for BMI is also collected every 6`th week during the hospitalization period.

Primary outcome

- Oxygen uptake: Is measured as VO₂peak during a maximal exercise test and is gold standard for measuring aerobic capacity. For people with a SCI several test protocols have been used [36].

Secondary outcomes

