Bodyweight: Is measured as Body Mass Index (BMI) which is the most widely used outcome measure for measuring bodyweight in people with SCI. BMI is not sensitive enough to distinguish between fat mass and lean body mass nor overweight in people with SCI. Lowering the cut-off for overweight to 25kg/m² the sensitivity increases although this adjustment is not used consequently in the literature [39]. BMI is already collected as part of the existing routines every week and data for BMI every 6`th week until discharge will be included in the project. Some newly injured are admitted to primary rehabilitation several months after the time of injury, and the course of bodyweight may already have changed significantly since the time of injury. Therefore BMI at the time of injury is collected from the patient journal from the initial hospitalization during the acute stage and by asking the patient at admission to primary rehabilitation about the height and weight at the time of injury.

Body composition: Is determined by Dual energy x-ray absorptiometry (Dexa) which is gold standard for assessing obesity and body composition although cut-off values for people with SCI has not been established [39].

Metabolic profile: Consists of CRP as a marker for inflammation, BP, Lipid profile: Total cholesterol, Triglycerides, HDL cholesterol, LDL cholesterol which all are included in the International SCI Endocrine and Metabolic Function Basic Data Set, as well as Hemoglobin A1c as a marker for carbohydrate metabolism, and is included in the International SCI Endocrine and Metabolic Extended Data Set [40, 41]. The analysis will be performed on the basis of an already existing blood sample in the present clinical practice.

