The intervention study and follow up is performed as a pragmatic study and includes, with a few exceptions, all newly injured patients with SCI admitted to primary highly specialized rehabilitation at CSCI. Patients will be included during a time period of 18 months corresponding to approximately 50 – 60 patients. Due to the rareness of the morbidity a power calculation is not performed for the primary outcome prior to the intervention, but it is assumed that the total participant number in the intervention and in the historic control cohort, will be comparable to the existing scientific literature.

Numeric continuous data collected at admission, discharge and follow up is reported descriptively as mean and standard deviation together with 95% confidence intervals, or as median, upper and lower quartile as well as interquartile range. Changes over time is reported on the basis of paired ttest. In subproject 3 and 4 the reliability of the outcome measures is analyzed by paired t-test, Pearson's product moment correlation and coefficient of variation or Intraclass correlation coefficient between the test- retest sessions.

Recruitment of participants:

All newly injured patients who are admitted for rehabilitation at CSCI during the project period are included in the primary intervention study as it becomes a part of usual care during the project period. The patients are identified by the primary investigator through internal lists of all inpatients and future admissions. Information about the study is provided to the patients by the Ph.D student and informed consent is retrieved in order to use anonymized data relevant to the study. Likewise

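### CRP change from admission is tested on all pairs with no account of acute illness at the draw, so a fall could reflect resolving illness if such illness is commoner at admission than later

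*Combined protocol and SAP*

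**What the plan says.** The metabolic profile is described under Secondary outcomes: "Consists of CRP as a marker for inflammation, BP, Lipid profile", followed by the individual lipids and HbA1c. The same entry gives the source of the blood: "The analysis will be performed on the basis of an already existing blood sample in the present clinical practice". The Intervention section of the primary study describes it as an added volume: "A blood sample (5ml) will be collected at the same time as a standard blood sample related to standard rehabilitation is collected", so that one needlestick serves both purposes. Either way, the timing follows the routine draw.

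On visits, the Outcome measures section says "All outcome measures will be collected at admission, discharge and follow-up 6 months after discharge". On analysis, the Statistics section says "Changes over time is reported on the basis of paired ttest", with no rule specific to CRP. The primary study expects that "complete data sets from admission to follow up are expected for approximately 50-60 patients during this period".

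No section excludes, defers, flags or adjusts for infection or other acute illness at the draw. The clinical exclusions under Participants and eligibility criteria concern the VO2peak test in sub study 2, not blood sampling. The Sub study 1 text, which describes the historic control, lists no metabolic profile. Figure 1 is not available in the text reviewed, so that absence rests on the prose alone.

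**The concern.** CRP rises with acute infection, wounds and recent surgery as well as with the low-grade inflammation that is of cardiovascular interest. Admission is the baseline, and for many patients it comes fairly soon after injury. If more patients have an acute process then than at discharge or six months later, the paired difference contains a downward shift unrelated to patient education.

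Such conditions are expected in this population. The Introduction lists bladder and skin among the areas under continuous assessment, and decubitus is a named exclusion for the exercise test. The plan standardises conditions before the VO2peak test, and it collects BMI at the time of injury because weight may already have changed by admission. CRP has no comparable protection, and the text gives no historic-cohort CRP from which the natural course could be judged.

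The primary study is described as run "with the aim of decreasing cardiovascular risk". A fall in an inflammation marker within that study could easily be taken as support for the aim.

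**Working it through.** **No figure to reproduce.** The plan gives no sample size, power or effect figure for CRP, and no infection rates. What follows is an illustration of the planned test under a zero intervention effect.

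**From the documents:** 50–60 complete data sets (55 used here); paired t-test. A two-sided 5% level is inferred from the planned 95% confidence intervals, so the nominal chance of a significant fall is 2.5%.

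**Assumed:** background CRP log-normal with median 3 mg/L, log-SD 0.8, within-patient log correlation 0.7 and no true change; infection adds 30–120 mg/L (mean 75); infection status independent between visits; 10–30% infected at admission and 5% later.

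**Expected spurious fall in the mean** = mean increment × (rate at admission − rate later):

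- 10% to 5%: 75 × 0.05 = 3.75 mg/L
- 15% to 5%: 75 × 0.10 = 7.5 mg/L
- 20% to 5%: 75 × 0.15 = 11.25 mg/L
- 30% to 5%: 75 × 0.25 = 18.75 mg/L

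Simulated mean falls were 3.7, 7.5, 11.1 and 18.8 mg/L. The difference between visit medians is much smaller, 0.2 to 1.8 mg/L over the same range.

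**Chance of a significant fall with no intervention effect** (3,000–4,000 simulated trials per scenario; repeat runs differ by one or two percentage points):

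| Infected at admission / later | t-test, raw | t-test, log | Rank test (Wilcoxon) | t-test, log, illness-free pairs |
|---|---|---|---|---|
| equal (5%/5% or 15%/15%) | about 2% | about 2% | about 2–3% | about 3% |
| 10% / 5% | 13% | 13% | 8% | 3% |
| 15% / 5% | 37% | 34% | 20% | 2% |
| 20% / 5% | 64% | 58% | 40% | 3% |
| 30% / 5% | 94% | 92% | 80% | 2% |

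**Second set of assumptions** (log-SD 1.0, correlation 0.6, infection adding a median of 20 or 40 mg/L, 50–60 pairs). The raw t-test gives 2–3% at 10%/10%, 9–13% at 10%/5%, 43–58% at 20%/5% and 78–91% at 30%/5%. The log scale gives 37–51% at 20%/5%. Illness-free pairs again give 2–3%.

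**Pairs left after setting aside illness at either visit** = 55 × (1 − rate at admission) × (1 − rate later):

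- 10% / 5%: 55 × 0.90 × 0.95 = 47.0
- 20% / 5%: 55 × 0.80 × 0.95 = 41.8
- 30% / 5%: 55 × 0.70 × 0.95 = 36.6

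The bias is therefore driven by the difference in illness rates between visits. A change of scale reduces it but does not remove it; a rank test helps more than a log transformation.

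**The case against.** **Direction is assumed.** The bias needs acute illness to be commoner at admission than later, and no section says that it is. Patients may enter up to 12 months after injury, and the BMI entry notes that some arrive several months after it, which weakens the assumption for part of the cohort. This stands. The concern is conditional, and with equal rates it disappears. The plan as written, however, would not let a reader tell which case applies.

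**Reading a fall as reduced risk.** A reader might infer that the plan counts a CRP fall as lower cardiovascular risk. It does not say so: the entry is limited to "Consists of CRP as a marker for inflammation". The cardiovascular reading comes from the place of CRP in the metabolic profile and from the study aim. It is a foreseeable interpretation, not a stated one.

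**Size.** The figures follow from assumed inputs, and the mean is the most sensitive summary. The Statistics section already allows medians and quartiles for description, where the shift is small. This stands for description, but the test of change named there is still the paired t-test.

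**Conflicting sample sources.** The two descriptions of the blood sample might look contradictory. They can be read together as an extra volume taken at the same needlestick as a routine sample, and timing follows routine care on either reading.

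**Triglycerides.** One might extend the argument to meals and fasting. The documents do not describe fasting conditions, but silence does not show that fasting state went unrecorded, and no direction or size of bias has been established.

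**Timing of the remedy.** The outcome section states that this is a revised analysis plan and that some outcomes were not analysed as intended, so data collection had already taken place. Prospective recording at each draw is no longer possible, and a new analysis set would be post hoc. This stands and shapes the fix.

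**Limits of an illness-free analysis.** The return to 2–3% assumes perfect flagging and no other resolving inflammation, and it does not supply the missing control. This also stands.

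**Conclusion.** The point holds in conditional form. CRP is measured on or alongside a routine draw, and its change from admission is tested on all pairs, with no account of acute illness and no historic-cohort CRP in the Sub study 1 text. If acute infection or other resolving inflammation is more common at admission than later, the planned test can show a fall without any intervention effect.

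On assumed inputs with 55 pairs, the chance of that is about 13% at 10% versus 5% infected and 64% at 20% versus 5% on raw values, or 8% and 40% with a rank test, against about 2% when rates are equal. These figures show sensitivity to the difference in rates; they are not estimates for this trial.

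The documents do not support a claim that a spurious fall is certain, or that the plan equates a CRP fall with reduced risk. The point affects one component of one secondary outcome and leaves the primary outcome untouched. It still merits a change, because the remedy is cheap and without it a CRP change is hard to interpret.

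**What to change.** - From the existing medical record, identify acute infection, pressure ulcer, recent surgery or antibiotic treatment around each CRP draw. Fix the time window before looking at the CRP results.
- Analyse CRP on a log or rank scale.
- Report the paired change twice: for all pairs, and for pairs free of acute illness at both visits. Label the second analysis post hoc if it is added after data collection.
- Interpret a fall as lower inflammation related to cardiovascular risk only if it persists in the illness-free pairs, and even then describe it as an uncontrolled pre-post change.
- State fasting status for triglycerides if the record gives it; otherwise report them as not standardised.
- Align the wording of the two descriptions of the blood sample, so that it is clear which sample is used at each visit.

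**Cost:** SAP wording and some chart review, with no new procedure for patients. The illness-free analysis has fewer pairs, about 42 of 55 at 20% versus 5%, and so less precision. Incomplete records would leave some misclassification, so the all-pairs result should stay alongside it.

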Therefore, the cardiovascular risk factor, including consequences of an inactive lifestyle and weight gain during and after the primary rehabilitation, defines the primary systematic approach in the current controlled study and sub-investigations.

The course of overweight

The prevalence of overweight among people with SCI is high and is conservatively estimated to

66% [2]. In a Swedish cohort of wheelchair dependent people with paraplegia, 27- 36% had a cardiovascular risk profile requiring treatment. When Body Mass Index (BMI) adjusted to SCI was entered into the risk model, 80% had a risk profile requiring treatment [3]. Energy expenditure decreases significantly the first weeks after injury and remains low throughout the primary rehabilitation, with the possibility of decreasing even more the following years. Body fat and body weight also decreases in the acute phase, before increasing in the subacute phase towards the same level as before the time of injury [4]. A longitudinal study with participants ranging from 19-60 years of age and neurological level AIS A-D (54% where incomplete at follow up), found an average loss of lean body mass corresponding to 20,5 and 15, 1% in the lower extremities and trunk respectively during the first year after injury. The course among people with SCI during and after discharge from the primary rehabilitation in Denmark is not known. BMI increases gradually, and especially during the first years after discharge from the primary rehabilitation. A Dutch prospective cohort study found that BMI increased gradually with a prevalence of overweight of 28 % during the primary rehabilitation and 54 % at follow up 5 years after discharge [5]. Similar inventories do not exist for people with SCI in Denmark. Obese people with SCI achieve a lower level of functioning during primary rehabilitation than people with normal weight [6], and more knowledge about prevention, treatment and managing overweight among people with SCI is warranted among health care professionals in the clinical setting. [7]. Overweight in people with SCI is associated with increased risk of depression, while physical activity may contribute to a decreased prevalence of depression and increased quality of life [8, 9]. The relationship between these variables in a Danish setting is not known.

Impact of physical activity on health and fitness

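### The paired BMI change from admission mixes natural regain after injury with any intervention effect, and the plan specifies no use of BMI at injury or time since injury

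*Combined protocol and SAP*

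**What the plan says.** The Statistics section handles all continuous outcomes in one paragraph: "Numeric continuous data collected at admission, discharge and follow up is reported descriptively", either by means with SDs and confidence intervals or by medians with quartiles. For change it says: "Changes over time is reported on the basis of paired ttest". It defines no baseline and names no covariate. It mentions no comparison with the historic cohort, and it gives no role to BMI at injury, time since injury or the six-weekly BMI values.

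Other sections describe why the starting point matters:

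- **The course of overweight:** weight is lost and then regained towards its pre-injury level: "Body fat and body weight also decreases in the acute phase, before increasing in the subacute phase towards the same level as before the time".
- **Participants and eligibility criteria:** patients injured up to 12 months earlier may enter.
- **Sub study 1, and Bodyweight under Secondary outcomes:** some patients arrive several months after injury. The Bodyweight paragraph adds that "the course of bodyweight may already have changed significantly since the time of injury". For this reason BMI at injury is obtained from the acute-stage record and by asking the patient.
- **Bodyweight, same paragraph:** "BMI is not sensitive enough to distinguish between fat mass and lean body mass nor overweight in people with SCI".

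Sub study 1 serves as the historic control. At CSCI it records BMI at admission, discharge and 6 months after discharge, and every six weeks during the stay. It lists DEXA only at discharge.

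**The concern.** Admission is not a common starting point. A patient admitted soon after injury may still be losing weight or be near the lowest point, while one admitted months later may already have regained part of the loss. A paired comparison that starts at admission therefore contains a stretch of the natural course, and how much depends on when each patient arrived. The protocol recognises this and collects a variable to deal with it, but the analysis text gives that variable no task.

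Two errors could follow. Ordinary regain could be read as a failure to prevent weight gain, or a real benefit could be cancelled by regain and go unseen. BMI is a secondary outcome, so the VO2peak result is not touched. Still, the Sub-investigations section treats BMI as a high-risk determinant and builds the national survey around it, and the primary study's stated aim is lower cardiovascular risk.

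**Working it through.** **Plan figure.** There is none to reproduce. The plan gives no expected BMI change, SD or significance level, and it says that "a power calculation is not performed for the primary outcome prior to the intervention". The calculations below illustrate scale only. From the documents come the cohort size ("Patients will be included during a time period of 18 months corresponding to approximately 50 – 60 patients"), the lengths of stay (averages of 85 to 123 days) and the 6-month follow-up. The regain, the SDs, the shape of the course, the admission timing and the two-sided 5% level are assumptions.

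**Step 1. Paired test with no intervention effect.** Let d be the natural rise and s the SD of change. The t statistic has noncentrality (d/s)√n on n − 1 degrees of freedom. For example, with d = 0.5, s = 2.0 and n = 50, this is 0.25 × 7.07 = 1.77, which gives 41% rejection.

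| s (kg/m²) | n | d = 0.25 | d = 0.5 | d = 1.0 |
|---|---|---|---|---|
| 1.5 | 50 | 21% | 64% | 99.6% |
| 1.5 | 60 | 25% | 72% | 99.9% |
| 2.0 | 50 | 14% | 41% | 93% |
| 2.0 | 60 | 16% | 48% | 97% |
| 2.5 | 50 | 11% | 28% | 79% |
| 2.5 | 60 | 12% | 33% | 86% |

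**Step 2. A hidden benefit.** The expected paired change is natural rise plus intervention effect. A rise of +0.5 and an effect of −0.5 sum to 0, so the test would reject in only 5% of studies although the effect is real.

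**Step 3. Staggered admission, no intervention effect.** Simulation with 55 patients per cohort and 4,000 runs. Assumed: lowest weight at 2 months; full regain by 12 months; admission at 0.5 months plus an exponential delay with mean 1.5 months; stay of 2.8–4.1 months; measurement SD 1.3, so SD of change 1.3 × √2 = 1.84. The last column compares change from admission between two cohorts with the same admission timing, without covariates.

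| Dip (kg/m²) | Mean change, admission to follow-up | Rejects from admission | Rejects from injury | Rejects between cohorts |
|---|---|---|---|---|
| 0.5 | +0.29 | 20% | 5% | 5% |
| 1.0 | +0.58 | 63% | 7% | 5% |
| 1.5 | +0.86 | 91% | 9% | 5% |
| 2.0 | +1.15 | 99% | 12% | 5% |

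**Step 4. Injury as the only reference.** The low rates in the fourth column depend on assumed full regain by 12 months. Suppose instead BMI 26 at injury, 5–10% lost by admission and half of that regained by discharge. The loss is 26 × 0.05 = 1.3 to 26 × 0.10 = 2.6 kg/m². From admission to discharge the change is +0.65 to +1.3. From injury to discharge it is −0.65 to −1.3. With no intervention effect, the first looks like failure and the second like success.

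**Step 5. What a cohort comparison can detect.** For 80% power with 50–60 patients per cohort, the detectable difference is (1.960 + 0.842) × √(2/n): 0.56 SD of change at n = 50 and 0.51 at n = 60. With SDs of 1.5–2.5 this is 0.51 × 1.5 = 0.77 to 0.56 × 2.5 = 1.40 kg/m². At 70 admissions a year, the 10-month survey would see about 70 × 10/12 = 58 patients at CSCI before any losses, so these cohort sizes are on the generous side for the control.

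**The case against.** The strongest reply is that the study already has a remedy. The historic cohort has BMI at the same time points and BMI at injury, and a natural course shared by both cohorts cancels in a comparison between them (last column of Step 3). This stands. A reader might infer that BMI change cannot show anything about risk reduction; the documents do not support that. The reply does not rescue the plan as written, because the Statistics section specifies no such comparison. Cancellation also needs similar admission timing in the two cohorts. Nothing in the documents suggests that timing differs, but nothing secures that it does not.

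A reader might also infer that BMI at injury is excluded from analysis. That would rest on silence in one generic paragraph. Because it is gathered at admission, it could even be read as falling under data collected at admission. What can be said is that it has no analysis specified.

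A third tempting step is to make BMI at injury the baseline. Step 4 shows that this can turn a bias against the intervention into one in its favour. It also counts an interval before admission, when no patient had been exposed to the intervention, and some of the values are recalled.

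Finally, a reader might try to size the fat gain hidden behind a stable BMI from the first-year lean-mass losses quoted in the background (20.5% legs, 15.1% trunk). Those losses run from injury, not from admission, and the documents give no lean mass in kilograms, so no such size can be claimed. The protocol itself states BMI's limits and lists DEXA and metabolic profile beside it. It nowhere says that a risk conclusion will rest on BMI alone.

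**Conclusion.** The point holds as a gap in specification with a real consequence. Following the Statistics section as written yields a paired BMI change that cannot be attributed to the intervention, because it contains natural regain in an amount that varies with time from injury to admission. The protocol describes both facts and collects BMI at injury because of them, but specifies no use of it.

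The documents do not fix the size. Under the assumed rises of 0.25–1.0 kg/m² and SDs of 1.5–2.5, the paired test would be significant in 11% to 99.9% of studies without any intervention effect. The regain runs against the hoped-for direction, so a hidden benefit is as much a risk as a misread rise.

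The conclusion concerns a secondary outcome. It does not extend to a claim that the study is unable to evaluate BMI.

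**What to change.** - **Main BMI analysis:** compare BMI at discharge and at 6 months between the intervention cohort and the CSCI part of the historic cohort, since the intervention runs only at CSCI. Adjust for admission BMI, BMI at injury and days from injury to admission. Because weight falls and then rises, let the term for days be curved.
- **Descriptive summaries:** keep the paired change from admission, and report BMI relative to injury beside it. Neither should carry the conclusion.
- **Body composition:** read BMI together with DEXA fat mass. As Sub study 1 lists DEXA only at discharge, fat mass can be compared between cohorts at discharge but not as change.
- **Labelling:** the document calls itself a revised plan and says that some outcomes were not analysed as intended. State when the BMI model was added, and show the paired results as well, so that it is not taken for a choice made after seeing the data.

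The cost is analysis-plan text and no new BMI measurement. Recalled heights and weights add noise to BMI at injury. The injury date is not listed as a data item and must be taken from the record used to apply the 12-month eligibility rule. Adjustment does not remove other differences between the two periods, and Step 5 shows that only fairly large BMI differences would be detected reliably without it. The adjusted model itself was not simulated here.
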